6.2. Exclusion Criteria

6.2.1. Exclusion Criteria for Healthy Participants and Bystanders

Participants are excluded from the study if any of the following criteria apply:

Medical Conditions

1. Alanine transaminase (ALT) >1.5x upper limit of normal (ULN)

- 2. Bilirubin >1.5xULN (isolated bilirubin >1.5xULN is acceptable if bilirubin is fractionated and direct bilirubin <35%).
- 3. Current or chronic history of liver disease, or known hepatic or biliary abnormalities (with the exception of Gilbert's syndrome or asymptomatic gallstones)
- 4. QTc > 450 msec

NOTES:

- The QTc is the QT interval corrected for heart rate (HR) according to Fridericia's formula (QTcF), machine-read or manually over-read.
- The specific formula that will be used to determine eligibility and discontinuation for an individual participant should be determined prior to initiation of the study. In other words, several different formulae cannot be used to calculate the QTc for an individual participant and then the lowest QTc value used to include or discontinue the participant from the trial.
- For purposes of data analysis, QTcF will be used as specified in the RAP.
- 5. Exclusion criteria for screening ECG (a single repeat is allowed for eligibility determination):

	Males	Females
Heart rate	<40 and >100 bpm <50 and >100 bpm	
PR Interval	<120 and >220 msec	
QRS duration	<70 and >120 msec	
QTcF interval	>450 msec	

6. Any clinically significant central nervous system (e.g., seizures), cardiac, pulmonary, metabolic, renal, hepatic or gastrointestinal conditions or history of such conditions that, in the opinion of the investigator may place the participant at an unacceptable risk as a participant in this trial or may interfere with the absorption, distribution, metabolism or excretion of drugs.

Prior/Concomitant Therapy

7. Past or intended use of over-the-counter or prescription medication (including herbal medications) within 7 days (or 14 days if the drug is a potential enzyme inducer) or 5 half-lives (whichever is longer) prior to dosing until completion of the follow-up visit, unless in the opinion of the Investigator and sponsor the medication will not interfere with the study. Specific medications listed in Section 7.7 may be allowed.

Prior/Concurrent Clinical Study Experience

- 8. Participation in the study would result in loss of blood or blood products in excess of 500 mL within 3 month period.
- 9. Exposure to more than 4 new chemical entities within 12 months prior to the first dosing day.

10. The participant has participated in a clinical trial and has received an investigational product within the following time period prior to the first dosing day in the current study: 3 months, 5 half-lives or twice the duration of the biological effect of the investigational product (whichever is longer).

Diagnostic assessments

- 11. Hemoglobin (Hgb) below the lower level of the normal range with one repeat testing allowed, or known hemoglobinopathies.
- 12. Known severe hypersensitivity reactions such as Stevens-Johnson Syndrome, toxic epidermal necrolysis, and erythema multiforme.
- 13. Presence of Hepatitis B surface antigen (HBsAg) at screening, Positive Hepatitis C antibody test result at screening.

NOTE: Participants with positive Hepatitis C antibody due to prior resolved disease can be enrolled, only if a confirmatory negative Hepatitis C RNA test is obtained

14. Positive Hepatitis C RNA test result at screening or within 3 months prior to first dose of study treatment

NOTE: Test is optional and participants with negative Hepatitis C antibody test are not required to also undergo Hepatitis C RNA testing

- 15. Positive pre-study drug/alcohol screen
- 16. Positive HIV antibody test
- 17. Regular use of known drugs of abuse

Other Exclusions

- 18. Male partners of women who are pregnant or lactating
- 19. Regular alcohol consumption within 3 months prior to the study defined as:
 - an average weekly intake of >21 units for males or >14 units for females. One unit is equivalent to 8 g of alcohol: a half-pint (~240 ml) of beer, 1 glass (125 ml) of wine or 1 (25 ml) measure of spirits.
- 20. Breath test indicative of smoking at day -1.
- 21. History of sensitivity to any of the study medications, including CCI15106 or components thereof and, for cohorts that will undergo BAL, those that may be used in association with the BAL procedure or components thereof or a history of drug or other allergy that, in the opinion of the investigator or Medical Monitor, contraindicates their participation.
- 22. For cohorts that will undergo BAL, contraindications to bronchoalveolar lavage including hypercapnia >50 mm Hg, abnormal blood coagulation parameters, known or suspected intolerance of medications necessary for bronchoscopy, refractory hypoxemia, reactive airway disease or asthma, unstable angina or acute myocardial infarction.
- 23. Documented lactose allergy/intolerance for dosing cohorts.

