	and lacrimation. Several cases of bronchospasm and/or chest pain have been reported, usually in individuals with reactive airways disease. Seven cases are known in which nurses administered Virazole dry substance during pregnancy (n=6) or just before conception (n=1). In 6 cases, healthy children were born. In one case, a chromosomal translocation was reported with mild developmental delay.	

Exposure risk for additional medications administered in the study (Salbutamol):

See package leaflet (https://www.medicines.org.uk/emc/PIL.22837.latest.pdf).

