- The planned dose frequency or duration may be modified based on emerging safety/tolerability and PK data from previous cohorts. The total daily dose will not exceed 120 mg.
- The number of cohorts may be reduced or expanded if needed.

- All participants in Part 1 Cohort B and in Part 2 Cohort B (60 mg BID dose for both Cohorts) will undergo BAL once during the study on days 10, 11, 12, or 13 after the first (morning) dose. Based on the lung ELF concentrations of CCI15106 observed, additional double-blinded, single-blinded or open-label repeat dose cohort(s) may be added at a dose not to exceed 120 mg daily. The total number of participants will not exceed that specified in Section 5.2.
- BAL may be used in the additional cohorts to obtain a more accurate estimation of the dose to lung exposure ratio and provide data for future dose predictions.

There will be approximately 3 cohorts of healthy participants in this study and approximately 2 cohorts of participants with moderate COPD. Participants in the dosing cohorts will be randomized to receive either CCI15106-IP or matching Liquidia particles without the active ingredient (lactose:polyvinyl alcohol 98:2 w/w 0.9x1 µm cylinder shape amorphous particles, referred to as placebo). Participants in Cohort C will be assigned to participants in Cohort B on a one to one basis for the entire duration of the study.

Screening visit will occur within 30 days of dosing for cohorts in Part 1 and within 45 days of dosing for cohorts in Part 2.

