For Cohort A Part 1, 60 mg single dose will be administered on Day 1; 120 mg single dose will be administered on Day 3; and then 30 mg dose will be administered BID on Days 6-19. Participants will report to the unit on Day -1 for assessments and randomization (randomization can also be done on Day 1, prior to dosing). Participants will be dosed the following morning on Day 1 followed by post-dose assessments. Blood for PK assessments will be collected for the next 48 hours (h). On Day 3 (after collection of 48 h PK time point), participants will receive a single dose of 120 mg followed by post-dose assessments and PK assessments for the next 72 h. Repeat dosing will begin on the morning of Day 6 (after collection of 72 h PK time point) and will continue for 14 days BID. Participants will remain in the unit for additional 2 days until 72 h PK timepoint is collected. Dosing frequency and duration may be adjusted based on emerging safety and tolerability data. Participants will return for the follow-up visit approximately 30 days after discharge. All male participants will also be called approximately 7 months after the follow-up visit to ensure no partner pregnancy.

For Cohort B Part 1, Repeat Dose SoA will be followed for the duration of the study. Participants will report to the unit on Day -1 for assessments and randomization (randomization can also be done on Day 1, prior to dosing). Dosing will begin on the morning of Day 1 and continue for 14 days BID. Dosing frequency and duration may be adjusted based on emerging safety and tolerability data. BAL procedure will be performed as soon as possible (within 1 h) after the first (morning) dose on one of the following days: 10, 11, 12, or 13. Participants will be discharged on Day 15 following completion of all post-dose assessments after the last dose, or later if additional PK collection or other assessments are required. Participants will return for the follow-up visit approximately 30 days after discharge. All male participants will also be called approximately 7 months after the follow-up visit to ensure no partner pregnancy.

For Cohort C Part 1, 14 healthy participants will be enrolled to evaluate bystander exposure and will follow Cohort C Part 1 SoA. Bystanders and air exposure will be evaluated concomitantly with Cohort B Part 1. Bystanders will report to the unit on Day

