6.1. Inclusion Criteria

6.1.1. Inclusion Criteria for Healthy Participants and Bystanders

Participants are eligible to be included in the study only if all of the following criteria apply. Rescreening is allowed only if approved by the Medical Monitor.

Age

1. Participant must be 18 to 65 years of age inclusive, at the time of signing the informed consent.

^{*} human systemic AUC(0-24) is predicted from a mechanistic model [Weber, 2017]

^{**} BD - twice daily dosing; AUC(0-24) on Day 14

Type of Participant and Disease Characteristics

- 2. Participants who are overtly healthy as determined by medical evaluation including medical history, physical examination, laboratory tests, and cardiac monitoring.
- 3. A participant with a clinical abnormality or laboratory parameter(s) which is/are not specifically listed in the inclusion or exclusion criteria, outside the reference range for the population being studied may be included only if the investigator (in consultation with the Medical Monitor if required) decide and document that the finding is unlikely to introduce additional risk factors and will not interfere with the study procedures.

Weight

4. Body weight ≥50 kg for males and 45 kg for females and body mass index (BMI) within the range 19 to 31 kg/m² (inclusive) for males and 17 to 31 kg/m² (inclusive) for females

Sex

5. Male OR Female

a. Male participants:

A male participant with female partner of child bearing potential must agree to use contraception as detailed in Appendix 5 of this protocol during the treatment period and for at least 7 months after the last dose of study treatment and refrain from donating sperm during this period.

b. Female participants:

A female participant is eligible to participate if she is not pregnant (see Appendix 5), not breastfeeding, and not a woman of childbearing potential (WOCBP) as defined in Appendix 5.

Informed Consent

6. Capable of giving signed informed consent as described in Appendix 3 which includes compliance with the requirements and restrictions listed in the informed consent form (ICF) and in this protocol.

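### The only healthy-volunteer exclusion that names reactive airway disease or asthma is tied to bronchoscopy, so bystanders in that risk group are covered only by general, partly discretionary criteria

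*Protocol*

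**What the plan says.** All references are to the latest protocol version in the file (document number ending _02).

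- **Section 6.2.1, criterion 22.** It begins "For cohorts that will undergo BAL, contraindications to bronchoalveolar lavage including hypercapnia >50 mm Hg, abnormal blood coagulation parameters" and its list ends with "refractory hypoxemia, reactive airway disease or asthma, unstable angina or acute myocardial infarction". Nowhere else in the healthy-participant and bystander list is asthma or reactive airway disease named.
- **Section 5.1, who has lavage.** "All participants in Part 1 Cohort B and in Part 2 Cohort B (60 mg BID dose for both Cohorts) will undergo BAL once". Cohort A Part 1 and Cohort C are not among these cohorts.
- **Section 5.1, the bystanders.** "For Cohort C Part 1, 14 healthy participants will be enrolled to evaluate bystander exposure".
- **Section 3.3.1, bystander row.** On people giving direct care to infants receiving aerosolized drug, it reports: "Several cases of bronchospasm and/or chest pain have been reported, usually in individuals with reactive airways disease". The mitigation column lists air and bystander measurements, staff leaving the room, warnings and training, and not enrolling women of child-bearing potential. It does not mention airway disease.
- **General criteria that reach every bystander.** Inclusion 2 requires "Participants who are overtly healthy as determined by medical evaluation including medical history, physical examination, laboratory tests, and cardiac monitoring". Inclusion 3 admits an abnormality not named in the criteria only if the investigator documents that it is unlikely to add risk. Exclusion 6 covers clinically significant "cardiac, pulmonary, metabolic, renal, hepatic or gastrointestinal conditions or history of such conditions that, in the opinion of the investigator" meet a risk or drug-disposition test. Exclusion 7 bars recent or intended medication, with an exception at the discretion of investigator and sponsor.
- **Section 2, schedules.** Screening spirometry is for participants with COPD only. The Cohort C schedule contains no spirometry.

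**The concern.** The protocol names a susceptible group for bystander exposure and has an exclusion that names the same group, but the two do not meet. The exclusion is attached to the bronchoscopy, which bystanders do not have, and not to the inhaled exposure, which they do have.

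Two things are at stake. The first is safety. Bystanders load and pierce the capsules, open the used devices, and sit within about 1 m of the doser beside open devices and spent capsules, while staff stay outside the room until at least 15 minutes after dosing (Sections 7.5 and 9.4.8.2). The second is interpretation. Bystander safety has its own analysis population (Section 10.2). If a bystander with mild or past asthma wheezes, there is no scheduled lung function value from before exposure to help separate secondary exposure from the pre-existing condition.

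**Working it through.** The protocol gives no figure on this point, so the check is mainly a comparison of texts.

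**Step 1: does criterion 22 reach Cohort C?** It applies only to cohorts that undergo lavage. Section 5.1 assigns lavage to Part 1 Cohort B and Part 2 Cohort B. Cohort C is not covered by it. Neither is Cohort A Part 1, whose participants inhale study treatment directly.

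**Step 2: what do the general criteria leave open for a bystander?**

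| Criterion | What it should stop | What it leaves open |
|---|---|---|
| Inclusion 2 | Disease evident from history or examination | Its listed evaluation includes no lung function test |
| Inclusion 3 | Unnamed abnormalities that may add risk | Admission on documented investigator judgement; for a bystander, asthma is arguably not a named condition |
| Exclusion 6 | Clinically significant pulmonary disease or a history of it | Disease judged not clinically significant, or not meeting the test "that, in the opinion of the investigator may place the participant at an unacceptable risk as a participant in this trial" or the drug-disposition test, which has little bearing on someone who is not dosed |
| Exclusion 7 | Much treated asthma | Untreated or intermittent disease outside the look-back of 7 days (14 for potential enzyme inducers) or 5 half-lives; also the investigator and sponsor exception |

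The residual group is therefore mild, intermittent or past disease that the investigator judges not clinically significant.

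**Step 3: is there baseline lung function?** For Cohort C there is none, at screening or later. Cohort A Part 1 differs. It has no screening spirometry, but it follows the single-dose schedule on Day 1, which includes a pre-dose reading. The missing baseline is thus a bystander problem, while the missing named exclusion is common to both cohorts.

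**Step 4: amount of exposure.**
- Dosing sessions per bystander: 14 days × 2 = 28.
- All bystander sessions: 14 × 28 = 392.
- Sessions with an assigned partner on active drug, with 12 active and 2 placebo in Cohort B: 12 × 28 = 336.

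Two pairs share the room at a time, so a bystander paired with a placebo doser may still be exposed through the other pair. The documents do not allow an estimate of how many bystanders would have mild or past asthma.

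**The case against.** The strongest reply is that the general criteria already do this work. An investigator who has read the risk table must find each bystander healthy, must document why any unnamed abnormality adds no risk, and must exclude significant pulmonary disease or a history of it. Treated asthma would mostly fail exclusion 7. Criterion 22 is correctly scoped for what it is, a list of bronchoscopy contraindications, and the bystander mitigation column never promises an asthma exclusion, so there is no outright contradiction. The risk-table sentence concerns caregivers of infants on a nebulised product, says usually and not always, and joins bronchospasm with chest pain. The doses also differ: at most 120 mg a day per doser here against 6 g for the inhaled marketed product, a ratio of 6,000 / 120 = 50. Section 3.3.1 adds that dry powder carries less acute lung risk than a low-osmolarity nebulised solution.

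Most of this stands, and it limits the point. Three stronger readings that a reader might infer are not supported:

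- *That asthmatic bystanders can freely be enrolled.* Inclusions 2 and 3 and exclusions 6 and 7 say otherwise for significant or treated disease.
- *That neither selection nor monitoring covers the risk.* Section 9.4.5 provides for further spirometry when symptoms suggest bronchospasm, and does not limit this to dosed participants. Bystanders also have adverse event review, physical examinations on Day -1 and Day 15 that include the lungs, and vital signs with respiratory rate two hours after the morning exposure on eight days. Staff watch through the door.
- *That the bystander results would be uninterpretable.* The primary bystander exposure endpoints are plasma concentration and filter amount, and nothing in the documents suggests that asthma distorts them. Medical history and participant-level listings would identify an affected person.

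Nor is it sound to assume a population asthma prevalence and compute the chance that at least one of 14 bystanders is affected. The documents give no prevalence, and the calculation would ignore the screening just described.

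The reply does not explain why the one group that the bystander row singles out is named for exclusion only where bronchoscopy is planned. Symptom-triggered spirometry also has no pre-exposure value in a bystander to compare with.

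**Conclusion.** The point holds as a mis-scoped eligibility rule. For Cohort C, and for dosed Cohort A Part 1, reactive airway disease or asthma is covered only by general and partly discretionary criteria, although the protocol's own bystander risk row identifies that group and offers no mitigation for it.

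The gap is limited to mild, intermittent or past disease judged not clinically significant. If such a bystander had an airway event, attribution to secondary exposure would be difficult but not impossible. No sample size, endpoint or planned analysis is affected. The conclusion assumes that Cohort C has no lavage, as Section 5.1 states, and that investigators may differ on what is clinically significant in someone who is not dosed. It warrants a cheap improvement, not a redesign.

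**What to change.** Reconcile Section 6.2.1 with the bystander row of Section 3.3.1. Take the existing wording on reactive airway disease or asthma out of criterion 22 and list it separately, with a scope that follows the exposure hazard and therefore includes Cohort C. The sponsor should state whether Cohort A Part 1 falls under it as well. The wording must continue to apply to the lavage cohort, and the other lavage contraindications stay in criterion 22 unchanged. Refer to the separated criterion in the mitigation column of the bystander row, so that the hazard and the safeguard appear together.

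The cost is one eligibility line and one table entry. No new procedure is needed, because medical history is already taken at screening. The downside is slightly fewer eligible volunteers.

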6.2.2. Exclusion Criteria for Participants with COPD

- 1. Alanine transaminase (ALT) >1.5x upper limit of normal (ULN)
- 2. Bilirubin >1.5xULN (isolated bilirubin >1.5xULN is acceptable if bilirubin is fractionated and direct bilirubin <35%).
- 3. Current or chronic history of liver disease, or known hepatic or biliary abnormalities (with the exception of Gilbert's syndrome or asymptomatic gallstones).
- 4. QTc > 450 msec or QTc > 480 msec in participants with Bundle Branch Block NOTES:
 - The QTc is the QT interval corrected for HR according to Fridericia's formula (QTcF), machine-read or manually over-read.
 - The specific formula that will be used to determine eligibility and discontinuation for an individual participant should be determined prior to initiation of the study. In other words, several different formulae cannot be used to calculate the QTc for an individual participant and then the lowest QTc value used to include or discontinue the participant from the trial.
 - For purposes of data analysis, QTcF will be used as specified in the RAP.
- 5. Participant has poorly controlled COPD, defined as the occurrence of **either** of the following:
 - Acute worsening of COPD requiring use of antibiotics or systemic corticosteroids in the 6 weeks prior to screening visit **OR**
 - More than 2 exacerbations of COPD requiring treatment with oral steroids in the preceding year or hospitalization for the treatment of COPD within 3 months of screening or more than twice during the preceding year.
- 6. History of an upper or lower respiratory tract infection requiring antibiotics in the 4 weeks prior to screening
- 7. Participant has a diagnosis of active tuberculosis, lung cancer, or any other respiratory condition that might, in the opinion of the Investigator, compromise the safety of the participant or affect the interpretation of the results. Participants with other respiratory disorders (e.g. **clinically significant:** asthma, pulmonary fibrosis, bronchiectasis) are excluded if these conditions are the primary cause of their respiratory symptoms.
- 8. Unstable or uncontrolled cardiac disease.
- 9. Participants who have past or current medical conditions or diseases that are not well controlled and, which as judged by the Investigator, may affect participant safety or influence the outcome of the study. (Note: Patients with adequately treated and well controlled concurrent medical conditions (e.g. hypertension) ARE permitted to be entered into the study).

Prior/Concomitant Therapy

10. Participants are not allowed to take oral corticosteroids from 4 weeks prior to screening and for the duration of the study.

- 11. Participants taking medications for any chronic conditions have to be on stable doses for 4 weeks prior to screening and until after completion of the treatment period. This includes COPD maintenance therapies (e.g. inhaled corticosteroids, long-acting beta-agonists, long-acting muscarinic agonists).
- 12. Didanosine and azathioprine are not allowed.
- 13. Use of short-acting inhaled bronchodilators is allowed, but participants must be able to discontinue their medications several times during the study as described in Section 7.7.
- 14. Use of long-acting bronchodilators is allowed, but participants must be able to modify the schedule of their medications twice during the study as defined in Section 7.7.

Prior/Concurrent Clinical Study Experience

- 15. Where participation in the study would result in donation of blood or blood products in excess of 500 mL within 3 months.
- 16. The participant has participated in a clinical trial and has received an investigational product within the following time period prior to the first dosing day in the current study: 3 months, 5 half-lives or twice the duration of the biological effect of the investigational product (whichever is longer).
- 17. Exposure to more than four new chemical entities within 12 months prior to the first dosing day.

Diagnostic assessments

- 18. Impaired renal function (eGFR <30 cc/min, using CKD-EPI equation).
- 19. Known severe hypersensitivity reactions such as Stevens-Johnson Syndrome, toxic epidermal necrolysis, and erythema multiforme.
- 20. Hgb below the lower level of the normal range with one repeat testing allowed or known hemoglobinopathies.
- 21. Presence of Hepatitis B surface antigen (HBsAg) at screening, Positive Hepatitis C antibody test result at screening.

NOTE: Participants with positive Hepatitis C antibody due to prior resolved disease can be enrolled, only if a confirmatory negative Hepatitis C RNA test is obtained

22. Positive Hepatitis C RNA test result at screening or within 3 months prior to first dose of study treatment

NOTE: Test is optional and participants with negative Hepatitis C antibody test are not required to also undergo Hepatitis C RNA testing

- 23. Positive pre-study drug/alcohol screen
- 24. Positive human immunodeficiency virus (HIV) antibody test
- 25. Regular use of known drugs of abuse

Other Exclusions

- 26. Male partners of women who are pregnant or lactating
- 27. Regular alcohol consumption within 3 months prior to the study defined as:
 - an average weekly intake of >21 units for males or >14 units for females. One unit is equivalent to 8 g of alcohol: a half-pint (~240 ml) of beer, 1 glass (125 ml) of wine or 1 (25 ml) measure of spirits.
- 28. Unable to refrain from smoking for 2 h prior to dosing and until all assessments are complete for 4 h after dosing and also for 1 h prior to any vital signs and ECG assessments
- 29. History of sensitivity to any of the study medications, including CCI15106 or components thereof and, for cohorts that will undergo BAL, those that may be used in association with the BAL procedure or components thereof or a history of drug or other allergy that, in the opinion of the investigator or Medical Monitor, contraindicates their participation.
- 30. For cohorts that will undergo BAL, contraindications to bronchoalveolar lavage including hypercapnia >50 mm Hg, abnormal blood coagulation parameters, known or suspected intolerance of medications necessary for bronchoscopy, refractory hypoxemia, reactive airway disease or asthma, unstable angina or acute myocardial infarction.
- 31. Documented lactose allergy/intolerance.

